The first primary objective is designed to assess if the immune response induced by 2 doses of MenABCWY is noninferior to the immune response induced by 1 dose of MenACWY-CRM, for ACWY-naïve and for ACWY-experienced participants separately. This will be assessed as the difference in the percentage of seroresponders, defined as participants achieving at least a 4-fold rise in hSBA titer from baseline for each ACWY test strain, 1 month after Vaccination 2 in Groups 1 and 3 separately (MenABCWY groups) compared to 1 month after Vaccination 1 in Groups 2 and 4 separately (MenACWY-CRM groups) using a noninferiority criterion of -10%. The first secondary immunogenicity objective is also designed to assess the noninferiority in MenA, MenC, MenW, and MenY responses in the MenABCWY groups compared to the MenACWY-CRM groups, using the same criterion; this comparison will be made 1 month after Vaccination 1 in Groups 1 and 3 separately (MenABCWY groups) compared to Groups 2 and 4 separately (MenACWY-CRM groups).

The second primary objective is designed to assess if the immune response for MenB induced by 2 doses of MenABCWY is noninferior to the immune response induced by 2 doses of Trumenba. This will be assessed using:

1. the differences in the percentage of participants achieving an hSBA titer \geq LLOQ (1:16 for strain A22 and 1:8 for strains A56, B24, and B44) for all 4 primary MenB test strains combined (composite response), in the MenABCWY groups compared to the Trumenba groups, at 1 month after Vaccination 2, and
2. the difference in the percentage of participants achieving at least a 4-fold rise in hSBA titer from baseline for each of the 4 primary MenB test strains, in the MenABCWY groups compared to the Trumenba groups, 1 month after Vaccination 2, using a noninferiority criterion of -10%. The second primary objective will be met if the noninferiority criterion is met for all these MenB endpoints.

The primary safety objective will be assessed by descriptive summaries of local reactions, systemic events, use of antipyretic medication, AEs, SAEs, NDCMCs, MAEs, and immediate AEs in the MenABCWY and Trumenba groups as described in [Section 9](#).

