9.1.2. Statistical Hypotheses

This study has 2 primary objectives and 1 secondary objective where hypothesis testing is applicable. The primary objectives are 1) to demonstrate that the immune response induced by 2 doses of MenABCWY is noninferior to the immune response induced by 1 dose of MenACWY-CRM, for ACWY-naïve and ACWY-experienced participants separately and 2) to demonstrate that the immune response for MenB induced by 2 doses of MenABCWY is noninferior to the immune response induced by 2 doses of Trumenba. The hypothesis testing for the secondary objective is to demonstrate that the immune response induced by 1 dose of MenABCWY is noninferior to the immune response induced by 1 dose of MenACWY-CRM, for ACWY-naïve and ACWY-experienced participants separately. Hypothesis testing for the secondary objective will be performed only if the primary objectives are successful.

For all objectives evaluating noninferiority of the immune response for MenA, MenC, MenW, and MenY, the definition of a seroresponder is a participant achieving at least a 4-fold rise in hSBA titer from baseline for each ACWY test strain, at the relevant analysis time point.

For the ACWY noninferiority evaluation in ACWY-naïve participants, the immune response will be evaluated at 1 month following Vaccination 2 for Group 1 and at 1 month following Vaccination 1 for Group 2. The null hypothesis (H_0) for each ACWY serogroup for noninferiority is as follows:

$$H_0: \pi_{G1} - \pi_{G2} \leq -10\%$$

where π_{G1} and π_{G2} are the percentages of participants who achieve a 4-fold rise in hSBA titers for MenA, MenC, MenW, and MenY for Group 1 and Group 2, respectively.

If the lower limit of the 2-sided 95% confidence interval (CI) for the difference in seroresponders (Group 1 – Group 2) is $> -10\%$ for all of the ACWY test strains (at 1 month after the second vaccination for Group 1 and at 1 month after the first vaccination for Group 2), the noninferiority of the MenABCWY regimen to the MenACWY-CRM regimen is declared for the ACWY-naïve participants.

For the ACWY noninferiority evaluation in ACWY-experienced participants, the approach will be identical to in ACWY-naïve participants, but Group 3 will be compared to Group 4, instead of Group 1 compared to Group 2. The noninferiority evaluations for both the ACWY-naïve and the ACWY-experienced participants are required to be successful to meet the first primary objective.

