The second primary objective will be evaluated at 1 month following Vaccination 2 and the post-Vaccination 2 evaluable population will be used. The null hypothesis (H_0) for noninferiority for each primary MenB test strain is as follows:

$$H_0: \pi_{G1+G3} - \pi_{G2+G4} \leq -10\%$$

where π_{G1+G3} and π_{G2+G4} are the percentages of 4-fold rises and composite responses for Groups 1 and 3 combined and for Groups 2 and 4 combined, respectively, at 1 month after the second vaccination.

If the lower limit of the 2-sided 95% CI for the differences in 4-fold rises and composite responses (Group 1+3 – Group 2+4) is $> -10\%$ for all of the primary MenB test strains at 1 month after the second vaccination, the noninferiority of the MenABCWY regimen to the Trumenba regimen is declared.

If noninferiority for both the primary objectives is demonstrated, then an additional noninferiority evaluation of the ACWY response will be performed. This evaluation will be a secondary objective and will be conducted as for the primary ACWY noninferiority assessment; however, the secondary objective will be an evaluation of noninferiority of seroresponders who achieve a 4-fold rise at 1 month following Vaccination 1 for both groups evaluated (Group 1 versus Group 2 for ACWY-naïve and Group 3 versus Group 4 for ACWY-experienced).

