9.1.3. Multiplicity Considerations

All the primary immunogenicity endpoints/estimands are considered coprimary in the study. For the primary immunogenicity objectives comparing immune responses induced by vaccine antigens from the MenABCWY group(s) to that from the comparator group(s), noninferiority is assessed by hypothesis tests as stated in [Section 9.1.2](#), at a 2-sided level of 0.05 for each of the endpoints. The primary immunogenicity objectives will be met if noninferiority is achieved for each endpoint. Therefore, the type I error rate for the immunogenicity assessment is well controlled at the 0.05 level. If the primary objectives are met, then testing of noninferiority for all the secondary endpoints related to seroresponders who achieve a 4-fold rise at 1 month after Vaccination 1 will be done at the 0.05 level.

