9.2. Sample Size Determination

9.2.1. Immunogenicity Subset (Groups 1-4)

[Table 7](#) and [Table 8](#) present the power to demonstrate that the immune response induced by 2 doses of MenABCWY is noninferior to the immune response induced by 1 dose of MenACWY-CRM for ACWY-naïve and ACWY-experienced participants, respectively, and [Table 9](#) presents the power to demonstrate that the immune response induced by 2 doses of MenABCWY is noninferior to the immune response induced by 2 doses of Trumenba. The study is powered based on a combined (product) power across both the primary objectives.

Noninferiority comparisons will be based on the 4-fold rises and also composite response for the MenB endpoints (at 1 month following Vaccination 2) and seroresponders who achieve a 4-fold response for the ACWY endpoints (at 1 month after Vaccination 2 for Groups 1 and 3 and at 1 month after Vaccination 1 for Groups 2 and 4). The lower bounds of the corresponding 95% CIs of the group differences will be compared to the noninferiority criterion (-10%).

With 360, 180, 540, and 270 evaluable participants in Groups 1, 2, 3, and 4, respectively, and the assumptions in the tables below, the power is:

- above 99.9% to demonstrate noninferiority for the first primary objective relating to the ACWY response in ACWY-naïve participants,
- above 99.4% to demonstrate noninferiority for the first primary objective relating to the ACWY response in ACWY-experienced participants, and
- above 91.6% for the second primary objective relating to the MenB response.

The combined power, across both primary objectives, is above 91.0%. Therefore, assuming a nonevaluable rate of 20%, 450, 225, 675, and 338 participants in Groups 1, 2, 3, and 4, respectively, will be enrolled to have sufficient evaluable participants.

Some participants may be moved from the safety subset to the immunogenicity subset as described in [Section 4.1](#). The sponsor may decide to proceed with less than full enrollment if an assessment of power shows that it is sufficient (<91% with full enrollment but still >85%) to meet the primary objectives. This assessment will be done in a completely blinded fashion before any participants are unblinded or the immunogenicity data are accessed.

Table 7. Power Analysis for First Primary Immunogenicity Objective (ACWY-Naïve Participants)

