9.4.1. Immunogenicity Analyses

Primary	
For each of the 4 ACWY test strains, the difference in the percentages of seroresponders, defined as participants achieving a 4-fold rise from baseline, in Group 1 at 1 month after Vaccination 2 compared to Group 2 at 1 month after Vaccination 1, and also the difference in seroresponders in Group 3 at 1 month after Vaccination 2 compared to Group 4 at 1 month after Vaccination 1, will be calculated.
 
For each of the 4 primary MenB test strains, the differences of the 4-fold rises and composite responses of Groups 1 and 3 combined compared to Groups 2 and 4 combined at 1 month after Vaccination 2 will be calculated.
 
The Miettinen and Nurminen method will be used to derive the CI for the difference in percentages between vaccine groups. The lower limit of the CI will be used in the hypothesis test for noninferiority as detailed in Section 9.1.
 
The analysis for the ACWY test strains is based on the post-Vaccination 1 evaluable population for Groups 2 and 4 and on the post-Vaccination 2 evaluable population for Groups 1 and 3 and the analysis for the primary MenB strains is based on the post-Vaccination 2 evaluable population in order to provide a comparison that has the greatest chance of identifying a difference between the groups with respect to immunogenicity, if a meaningful difference in vaccine effect actually exists.
 
Exact 2-sided 95% CIs for the percentages (seroresponders, 4-fold-rises and composite responses) will be provided using the Clopper-Pearson method.
 
A supportive analysis will be performed based on the modified intent-to-treat (mITT) population. Participants will be summarized according to the vaccine group to which they were randomized. Missing serology data will not be imputed.

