The null hypothesis (H_0) for noninferiority for each primary MenB test strain is as follows:

$$H_0: \pi_{G1+G3} - \pi_{G2+G4} \leq -10\%$$

where π_{G1+G3} and π_{G2+G4} are the percentages of 4-fold rises and composite responses for Groups 1 and 3 combined and for Groups 2 and 4 combined, respectively, at 1 month after the second vaccination.

The primary hypotheses for MenACWY endpoints and the primary hypotheses for MenB endpoints will be tested simultaneously. The primary objectives of noninferiority will be met only if all statistical criteria for the objectives were met. Therefore, the multiplicity of primary objectives does not require an alpha adjustment.

The secondary objective with hypothesis testing is:

- To demonstrate that the immune response induced by 1 dose of MenABCWY is noninferior to the immune response induced by 1 dose of MenACWY-CRM, for ACWY-naïve and ACWY-experienced participants separately.

Hypothesis testing for the secondary objective will be performed only if the primary objectives are successful.

The secondary objective of noninferiority will be met if:

- The lower limit of the 2-sided 95% CI for the difference in seroresponders (Group 1 - Group 2) is $> -10\%$ for all of the MenACWY test strains (at 1 month after the first vaccination for Group 1 and at 1 month after the first vaccination for Group 2); and
- The lower limit of the 2-sided 95% CI for the difference in seroresponders (Group 3 - Group 4) is $> -10\%$ for all of the MenACWY test strains (at 1 month after the first vaccination for Group 3 and at 1 month after the first vaccination for Group 4).

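### Each primary objective can be declared met on its own tests, but the case for no alpha adjustment covers only the rule that all 13 tests pass; a split result has no single prespecified conclusion

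*Protocol*

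**What the plan says.** Two sets of statements govern the same 13 primary noninferiority tests.

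**Objective by objective.**
- Protocol 9.1.2, four ACWY strains in naïve participants: if all pass, "the noninferiority of the MenABCWY regimen to the MenACWY-CRM regimen is declared for the ACWY-naïve participants". The experienced stratum follows by the same approach, and both strata must succeed for the first primary objective to be met. The MenB result is not mentioned.
- Protocol 9.1.2, MenB tests: if they pass, "the noninferiority of the MenABCWY regimen to the Trumenba regimen is declared".
- Protocol 1.1 (Statistical Methods): "The second primary objective will be met if the noninferiority criterion is met for all these MenB endpoints". The ACWY result is not mentioned.

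**All together.**
- Protocol 9.1.3 calls all primary immunogenicity endpoints coprimary, tests each "at a 2-sided level of 0.05 for each of the endpoints", and states: "The primary immunogenicity objectives will be met if noninferiority is achieved for each endpoint". It infers type I error control from that.
- SAP 5.1 joins the naïve, experienced and MenB criteria by a logical and, and states: "The primary objectives of noninferiority will be met only if all statistical criteria for the objectives were met". It gives this as the reason why no alpha adjustment is needed.

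Neither document says what may be concluded when one objective passes and the other fails.

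**The concern.** Requiring every test to pass protects one claim, the joint one. If any component null is true, the joint claim is false, and the chance of making it cannot exceed the level of that one test. The argument does not extend to two claims that can each be made while the other fails; then the chance of at least one false claim can exceed the level of either.

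The case at stake is a split result. If ACWY passes and one MenB endpoint misses, Protocol 9.1.2 has the first objective met and ACWY noninferiority declared, while SAP 5.1 has the primary objectives not met. If MenB passes and an ACWY strain misses, Protocol 1.1 has the second objective met and SAP 5.1 again says no. Choosing between these readings after the results are known would be post hoc.

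**Working it through.** **Inputs.** Margin −10 percentage points and evaluable numbers 360/180 (naïve), 540/270 (experienced) and 900/450 (MenB), from Protocol 9.2.1. Interval method from Protocol 9.4.1: "The Miettinen and Nurminen method will be used to derive the CI for the difference in percentages between vaccine groups". Only the lower limit of the 2-sided 95% interval is used, so each test is nominally one-sided 0.025. Stated powers are from Protocol Tables 7 to 9.

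**Step 1: the plan's own power.** The tests number 4 + 4 + 5 = 13.

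| Block | Stated | Recomputed, Miettinen-Nurminen, simulated |
|---|---|---|
| ACWY-naïve | >99.93% | 99.99% |
| ACWY-experienced | >99.45% | 99.68% |
| MenB | >91.63% | 91.82% |
| All 13 (product) | >91.0% | 91.5% |

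The stated blocks multiply to 0.9993 × 0.9945 × 0.9163 = 0.9106, and the stated MenB powers to 0.9803 × 0.9999 × 0.9564 × 0.9994 × 0.9780 = 0.9163. The plan's figures therefore reproduce. They are powers for the all-pass rule at one-sided 0.025, with endpoints multiplied as if independent.

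**Step 2: error of each rule.**
- Joint claim (all 13): at most 0.025.
- Either objective alone: at most 0.025, since each itself requires all its tests to pass (8 for ACWY, 5 for MenB).
- At least one false claim across the two objectives. Worst case: each has one endpoint exactly at −10% and the rest pass. If independent, 1 − (1 − 0.025)² = 0.0494. The bound for any correlation is 0.025 + 0.025 = 0.05.
- With correlation. The two objectives share participants. Assume a within-participant ACWY–MenB correlation ρ. The correlation between the experienced-stratum statistic and the pooled MenB statistic is then ρ√0.6, because 540/900 = 0.6. From the bivariate normal with critical value 1.96, ρ = 0.25 gives 0.0484 and ρ = 0.5 gives 0.0468. With the naïve stratum at the margin (ρ√0.4), ρ = 0.5 gives 0.0475.
- A simulation with Miettinen-Nurminen tests at the margin gave 0.0252 to 0.0262 per claim and 0.0502 for either of two. The 0.025 and 0.05 figures are therefore nominal sizes.

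**Step 3: how likely is a split?** Use the stated block powers.
- Both ACWY strata pass: 0.9993 × 0.9945 = 0.9938.
- MenB fails: 1 − 0.9163 = 0.0837 if the five endpoints are independent. If they are so strongly correlated that the weakest decides, only the B24 failure counts: 1 − 0.9564 = 0.0436.
- ACWY passes and MenB fails: 0.9938 × 0.0436 = 0.043 up to 0.9938 × 0.0837 = 0.083.
- MenB passes and ACWY fails: 0.9163 × (1 − 0.9938) = 0.006. From exact block powers of 0.99994, 0.9968 and 0.9190 it is 0.9190 × (1 − 0.99994 × 0.9968) = 0.003.

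The stated powers are printed as lower bounds, so these are approximate.

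**The case against.** The strongest reply is that the plan has one formal rule and keeps to it. The section devoted to multiplicity calls everything coprimary, power is a product over both objectives, the secondary test opens only if both succeed, and SAP 5.1 joins all criteria. On that view the declarations in Protocol 9.1.2 are intermediate results. This largely stands for the two ACWY strata, because 9.1.2 itself makes both necessary for the first objective. It does not dispose of the objective-level wording: Protocol 1.1 says outright when the second objective is met, and that sentence looks only at MenB. Protocol 9.1.3 can also be read one objective at a time; only SAP 5.1 rules that out.

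A second reply is that Protocol 9.1.3 speaks of control at 0.05, and the two-objective worst case is bounded by 0.05. But the stated level is two-sided and the decision uses one limit, so the matching level is 0.025.

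Three stronger readings are tempting but unsupported:
- That the separate declarations are uncontrolled. Each is held at nominal one-sided 0.025; only the rate across them is not.
- That the relevant figure is 1 − 0.975³ = 0.073 (bound 0.075). That counts the two ACWY strata as separate claims, whereas the protocol names two immunogenicity objectives.
- That SAP 5.1 forbids any claim after a partial pass. It says when the primary objectives are met and is silent on the rest.

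**Conclusion.** The point holds as an inconsistency in the decision rule. It is not an error in alpha, power or sample size: the joint rule, the secondary gate and the planned numbers are valid as written. The reason given for not adjusting alpha does not cover objective-level declarations. If these are used as confirmatory claims, the chance of at least one false claim is about 0.047 to 0.049, bounded by 0.05, against one-sided 0.025. That is a worst case, with both objectives false and each having one endpoint exactly at the margin; the lower end assumes a within-participant correlation of 0.5, which the documents do not give.

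The conflict is clearest for the second objective. In practice it is most likely to arise as ACWY passing and MenB failing, at roughly 4% to 8% under the planning assumptions, where the true value depends on the correlation among MenB endpoints. Protocol 9.2.1 also lets the sponsor proceed with combined power down to just above 85%, in which case missing full success, and so a split, becomes more likely.

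**What to change.** State one rule in Protocol 1.1, 9.1.2 and 9.1.3 and in SAP 5.1, before unblinding. Either of two would do.

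**(a) Joint claim only.** Describe the block results in Protocol 9.1.2, and the sentence in Protocol 1.1 on the second objective, as component criteria. Say that confirmatory noninferiority is declared only if all 13 tests pass, and that a partial pass is reported descriptively.

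**(b) Fixed sequence, if a claim after a partial pass is wanted.** Keep the same 2-sided 95% intervals and test in order: ACWY in both strata (all 8 tests); MenB (all 5); the secondary 1-dose ACWY objective. Declare a step only if every earlier step passed, and treat a single-stratum ACWY result as a component of the first step. This holds the family-wise error at one-sided 0.025, leaves the chance of full success and the secondary gate unchanged, and makes an ACWY claim valid when only MenB misses.

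The choice is one of claim strategy and belongs to the sponsor. Both options cost wording only: no participants, data or analyses. Option (a) gives up stand-alone claims. Option (b) gives up only a MenB claim when ACWY fails, about 0.3% to 0.6% under the planning assumptions, and the SAP's alpha argument does not support that claim in any case.

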9.1.3. Multiplicity Considerations

All the primary immunogenicity endpoints/estimands are considered coprimary in the study. For the primary immunogenicity objectives comparing immune responses induced by vaccine antigens from the MenABCWY group(s) to that from the comparator group(s), noninferiority is assessed by hypothesis tests as stated in [Section 9.1.2](#), at a 2-sided level of 0.05 for each of the endpoints. The primary immunogenicity objectives will be met if noninferiority is achieved for each endpoint. Therefore, the type I error rate for the immunogenicity assessment is well controlled at the 0.05 level. If the primary objectives are met, then testing of noninferiority for all the secondary endpoints related to seroresponders who achieve a 4-fold rise at 1 month after Vaccination 1 will be done at the 0.05 level.

9.2. Sample Size Determination

9.2.1. Immunogenicity Subset (Groups 1-4)

[Table 7](#) and [Table 8](#) present the power to demonstrate that the immune response induced by 2 doses of MenABCWY is noninferior to the immune response induced by 1 dose of MenACWY-CRM for ACWY-naïve and ACWY-experienced participants, respectively, and [Table 9](#) presents the power to demonstrate that the immune response induced by 2 doses of MenABCWY is noninferior to the immune response induced by 2 doses of Trumenba. The study is powered based on a combined (product) power across both the primary objectives.

Noninferiority comparisons will be based on the 4-fold rises and also composite response for the MenB endpoints (at 1 month following Vaccination 2) and seroresponders who achieve a 4-fold response for the ACWY endpoints (at 1 month after Vaccination 2 for Groups 1 and 3 and at 1 month after Vaccination 1 for Groups 2 and 4). The lower bounds of the corresponding 95% CIs of the group differences will be compared to the noninferiority criterion (-10%).

With 360, 180, 540, and 270 evaluable participants in Groups 1, 2, 3, and 4, respectively, and the assumptions in the tables below, the power is:

- above 99.9% to demonstrate noninferiority for the first primary objective relating to the ACWY response in ACWY-naïve participants,
- above 99.4% to demonstrate noninferiority for the first primary objective relating to the ACWY response in ACWY-experienced participants, and
- above 91.6% for the second primary objective relating to the MenB response.

The combined power, across both primary objectives, is above 91.0%. Therefore, assuming a nonevaluable rate of 20%, 450, 225, 675, and 338 participants in Groups 1, 2, 3, and 4, respectively, will be enrolled to have sufficient evaluable participants.

Some participants may be moved from the safety subset to the immunogenicity subset as described in [Section 4.1](#). The sponsor may decide to proceed with less than full enrollment if an assessment of power shows that it is sufficient (<91% with full enrollment but still >85%) to meet the primary objectives. This assessment will be done in a completely blinded fashion before any participants are unblinded or the immunogenicity data are accessed.

Table 7. Power Analysis for First Primary Immunogenicity Objective (ACWY-Naïve Participants)

Criteria	ACWY Test Strains	Reference Rate (Group 2) ^a	Assumed Difference (G1 – G2) ^a	Number of Evaluable Participants (Group 1)	Number of Evaluable Participants (Group 2)	Power ^b	Power to Meet NI for All Serogroups
Lower limit of 95% CI for the difference in seroresponders (Group 1 – Group 2) > -10%	MenA	95.8%	0	360	180	99.96%	
	MenC	70%	15%	360	180	>99.99%	
	MenW	75.9%	15%	360	180	>99.99%	
	MenY	71.9%	15%	360	180	>99.99%	
	Power (to meet NI for all ACWY test strains)						>99.93%

Abbreviations: ACWY = meningococcal groups A, C, W, and Y; G1 and G2 = Groups 1 and 2; MenA, MenC, MenW, and MenY = *Neisseria meningitidis* groups A, C, W, and Y; NI = noninferiority.

a. Reference Study B1971057, ACWY-naïve participants.

b. At 0.05 alpha level (2-sided).

Table 8. Power Analysis for First Primary Immunogenicity Objective (ACWY-Experienced Participants)

Criteria	ACWY Test Strains	Reference Rate (Group 3) ^a	Assumed Difference (G3 – G4) ^a	Number of Evaluable Participants (Group 3)	Number of Evaluable Participants (Group 4)	Power ^b	Power to Meet NI for All Serogroups
Lower limit of 95% CI for the difference in seroresponders (Group 3 – Group 4) > -10%	MenA	97%	-1%	540	270	>99.99%	
	MenC	95.8%	-1%	540	270	>99.99%	
	MenW	97%	-2%	540	270	99.98%	
	MenY	94.6	-2%	540	270	99.49%	
	Power (to meet NI for all ACWY test strains)						>99.45%

Abbreviations: ACWY = meningococcal groups A, C, W, and Y; G3 and G4 = Groups 3 and 4; MenA, MenC, MenW, and MenY = *Neisseria meningitidis* groups A, C, W, and Y; NI = noninferiority.

a. Reference Study B1971057, ACWY-experienced participants.

b. At 0.05 alpha level (2-sided).

Table 9. Power Analysis for Second Primary Immunogenicity Objective

Criteria	Endpoint	MenB Strain	Reference Rate (Groups 2 + 4) ^a	Assumed Difference (G1 and G3 Combined – G2 and G4 Combined)	Number of Evaluable Participants (Groups 1 + 3 Combined)	Number of Evaluable Participants (Groups 2 + 4 Combined)	Power ^b	Power to Meet NI for All Endpoints
Lower limit of 95% CI for the difference in 4-fold rises and composite responses (Groups 1 + 3 combined – Groups 2 + 4 combined) > -10%	hSBA titer fold rise ≥ 4 from baseline	A22	73.8%	0	900	450	98.03%	
		A56	95%	0	900	450	>99.99%	
		B24	64.5%	0	900	450	95.64%	
		B44	86.4%	0	900	450	99.94%	
	Composite response		72.9%	0	900	450	97.80%	
Power (to meet NI for all MenB endpoints)								>91.63%

Abbreviations: G1, G2, G3, and G4 = Groups 1, 2, 3, and 4; hSBA = serum bactericidal assay using human complement; Men B = *Neisseria meningitidis* group B; NI = noninferiority.

a. Reference Studies B1971057 and B1971012 (0-, 6-month schedule) for B24 and the composite response.

b. At 0.05 alpha level (2-sided).

There is over 90% power to demonstrate noninferiority for the secondary objective for ACWY-naïve and -experienced participants separately, evaluating the seroresponse for ACWY endpoints at 1 month following vaccination for each group.

